 235 demand for PMTCT and HIV services to be integrated within existing Maternal and Child Health (MCH)
 236 services.[112, 113]Home visits are designed for all pregnant couples (regardless of woman's initial HIV
 237 test result at the ANC clinic) and include topics important for maternal, paternal, and child health during
 238 pregnancy and postpartum. This approach capitalizes on men's heightened concern for family health
 239 during pregnancy,[114] and is more likely to engage men than approaches that focus solely on HIV-
 240 related health.

241

242 STUDY DESIGN/METHODOLOGY

[figure not shown]
243

244 A. Study design

245 To accomplish the study aims, we will conduct a three-arm couple-randomized trial of the home-based
 246 couples intervention in 24 communities in southwestern Kenya. We will recruit pregnant women (and
 247 subsequently their male partners) from ANC clinics, collect baseline questionnaire data, and randomize
 248 those who are willing to either the home-based couple intervention (estimated n=267 couples), the HIV
 249 self-test kits intervention (n=267 couples) or the standard care arm (estimated n=267 couples). Each
 250 arm will include 178 HIV-positive women at baseline and 89 HIV-negative women at baseline.

251 We will assess initial couples
 252 testing uptake and results with a
 253 brief phone-based assessment
 254 prior to birth and conduct follow-
 255 up assessments with both
 256 women and men at 3 and 12
 257 months after expected infant
 258 delivery date of the infant.
 259 Midline and final questionnaires
 260 will assess primary and
 261 secondary outcomes along with
 262 potential mediators. Brief phone
 263 assessments at 6 and 18
 264 months will ascertain the HIV
 265 status of infants and reconfirm

266 any couples testing behaviors (Fig 3). A subset of young women at or below age 24 years (n=30) and a
 267 subset of women who have experienced intimate partner violence (n=30) will be selected to participate
 268 in in-depth qualitative interviews following birth of their infants in order to gain in-depth understanding of
 269 how these factors (young age, IPV) affect women's postnatal healthcare utilization and secondary
 270 health outcomes. These in-depth interviews will also allow for a deeper understanding of the
 271 experiences of young women and women impacted by IPV in their healthcare utilization after delivery
 272 and how the intervention may have impacted Aim 2 outcomes.

[figure not shown]

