423 to 24. The additional six clinics are necessary because of the lower than anticipated participant
424 enrolment numbers due to COVID 19 pandemic and healthcare worker's strike that affected the
425 numbers of pregnant women visiting health facilities and consequently our study accruals in the year
426 2020 and 2021. Using a stratified randomized design, we will recruit HIV-negative women in balanced
427 numbers to HIV-positive women (1:2) each month, to ensure that these two groups are balanced over
428 time. Given our experience in the R34 pilot study (which had more stringent eligibility criteria), we
429 conservatively estimate a 75% participation rate for male partners in the study (target sample N=800
430 couples). If we subsequently experience as much as 17% loss-to-follow-up of couples (based on the
431 14% we experienced in the R34 pilot), we will still have approximately 664 couples (221 couples in
432 each randomized group) for analysis. With a loss-to-follow-up rate as high as 20% (leaving 640
433 couples), we will still have strong power to detect differences in our primary couples testing outcome
434 (Table 2).

435
436 Two groups of n=30 women each will be purposively selected from enrolled participants and invited to
437 participate in in-depth qualitative interviews. The samples will include women who are HIV-positive or -
438 negative and who participated in the different arms of the trial. One group will include women ≤24 years
439 of age, and the other group will comprise women of any age who have reported IPV at any time during
440 the trial.

441
442 **Recruitment and enrollment:** Pregnant women presenting at ANC clinics who meet study inclusion
443 criteria will be asked if they would like to participate in a study about approaches for supporting
444 pregnant couples on family health issues (including HIV) during pregnancy and postpartum. If
445 interested, informed consent will be obtained for study participation and for contacting her male partner.
446 Those interested in participating but not comfortable with face- to- face contact due to COVID -19
447 pandemic will be asked to participate remotely via the phone after safety and privacy has been
448 ascertained.

449
450 Postpartum women enrolled in the trial who are eligible to participate in the in-depth qualitative
451 interviews will be contacted by a researcher and invited to participate in an interview (at least 12

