	New male HIV+ tests	Number of new HIV+ test results of male partners*	
HEALTH CARE UTILIZATION	Discordant couples	Number of new serodiscordant couples identified	
	PMTCT practices	Mother's use of ARVs for PMTCT *, Prophylactic ARVs for the infant *, infant feeding practices	
	Use of MCH services	Number of ANC visits*, Childbirth with a skilled attendant (Y/N), Postnatal check-ups*	
	PREP uptake	Initiation of PrEP	
	Woman's HIV care linkage and engagement	Time to linkage in HIV care, *Enrollment in HIV care (Y/N), *Self-reported ART adherence, [160] Number of HIV visits*	
	Man's HIV care linkage	Time to linkage in HIV care, * Enrollment in HIV care (Y/N), * Self-reported ART adherence, [160] Number of HIV visits*	
	Infant HIV testing	Date and result of infant HIV test *	
	Intervention content	Topics covered, services delivered, referrals made during couple visits	
PROCESS MEASURES			All intervention participants at follow-up

Participation	Number of couple home visits completed, number of HIV self-tests received/used		
Social consequences	Positive and Negative Life Events measures[142]		
Acceptability	Satisfaction with intervention components, intervention content, and mode of delivery, attitudes toward PrEP and HIV self-testing		
SECONDARY HEALTH OUTCOMES	Viral suppression	Viral Load < 200 copies (undetectable)*	All HIV-positive participants at baseline and follow-ups
	HIV-free child survival	Child alive and HIV-free at 18 months after the birth*	

* Measures to be confirmed through medical records

536

537

538 Inclusion/exclusion criteria

539 Our inclusion criteria are: (a) women at 36 weeks of pregnancy or less (b) 15 years of age or older (c)
 540 has been offered HIV testing at ANC, (d) is currently in a stable relationship with a male partner and
 541 living with that male partner, (e) has not yet participated in couple HIV testing during this pregnancy,
 542 and (f) not in an HIV-positive concordant relationship Male partners are the person identified by the
 543 pregnant woman as her primary male partner and should also be 15 years of age or older.

544

545 STATISTICAL/ANALYSIS PLAN

546 Sample size and power calculations

547 The couple testing uptake outcome (primary outcome) will be assessed including both HIV-positive and
 548 HIV-negative women/couples. All three arms will be compared with each other (3 comparisons), so our
 549 Type I error rate is $0.05/3 = 0.017$ (two-sided). With three repeated measurements (baseline, 3 months,

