 550 and 12 months) and compound symmetry
 551 covariance structure, correlation between
 552 the observations on the same subject was
 553 assumed to be 0.50. With N=300 couples
 554 in each arm, our study will have >80%
 555 power to detect statistically significant
 556 differences in couple testing uptake of 30-
 557 40% either intervention arm and 23% in
 558 the control arm (Table 2). We
 559 conservatively used rates that are lower
 560 than proportions observed in the R34
 561 study and studies of HIVST kits with
 562 pregnant women. The secondary

563 outcomes are HIV-free child survival at 18 months and maternal viral load suppression at 18 months.
 564 HIV-free child survival up to 18 months will be assessed only in HIV-positive women with live births,
 565 with approximately N=200 in each arm. Based on prior estimates from sub-Saharan Africa,[161, 162]
 566 we expect proportions $\geq 90\%$ of HIV-free survivors in each arm. As there would be 2 comparisons (each
 567 intervention arm versus the control arm), we set our Type I error rate to $0.05/2 = 0.025$ (two-sided) when
 568 calculating power. If Arm 3 has a survival rate of 91%, the study will have power > 80% when Arms 1
 569 and 2 have survival rates of 98% or higher. The other secondary outcome of maternal viral load
 570 suppression at 18 months will be assessed only in HIV-positive women with around N=200 in each
 571 arm. From Table 2, if Arm 3 has a maternal viral load suppression rate of 85%, the study will have
 572 power > 80% when Arms 1 and 2 have maternal viral load suppression rates of 95% or higher. We
 573 used PASS software for these calculations (NCSS, version 11).

574

575 Data analysis

576 **Primary analyses to address Aim 1:** We will use all longitudinal measures of couple testing in a
 577 marginal model to compare rates among the three study arms. We will use a marginal modeling
 578 approach because our primary interest is to estimate the population-average effect of intervention
 579 participation on each outcome rather than the effect for a hypothetical average subject or couple.

Table 2. Statistical Power for Comparison of Outcomes Among Study Arms				
Couple Testing Uptake (assuming 23% uptake in the standard care arm (Arm 3)				
Proportion (%) of CHTC uptake in Arm 1 or 2	31	33	35	37
Corresponding Odds ratio (ref=Arm3)	1.50	1.65	1.80	1.97
Power (%) to detect a sig. difference among Arms at 0.017 level, auto-correlation (rho)=0.50	63	84	95	99

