813 according to study arm. Follow-up questionnaires will be conducted with women and male partners at 3
814 months and 12 months after the expected due date (EDD) of the infant. In addition, brief mobile phone
815 assessments of uptake of HIV testing and results will be conducted during late pregnancy and at 6
816 months after the birth, and a brief phone assessment of maternal and infant health outcomes will be
817 conducted at 18 months after the birth.

818

819 For AIM 2 qualitative interviews with two groups of n=30 women each, a subset of young women and a
820 subset of women with IPV will participate in a brief one-on-one interview during the postpartum period.

821

822 *Criteria for inclusion or exclusion:* The initial target populations are pregnant women identified in the
823 ANC clinics in the Nyanza Region of Kenya and their male partners. The vast majority (87%) of women
824 presenting for first ANC visits in Kenya are in the 2nd and 3rd trimesters of pregnancy, but given the
825 importance of early initiation of ART for maternal health and PMTCT, we will enroll women as early as
826 possible. We will select women at 36 weeks of pregnancy or less, to have time to deliver at least one
827 home visit during pregnancy. Other inclusion criteria are: (a) 15 years of age or older (b) has been
828 offered HIV testing at ANC, (c) is currently in a stable relationship with a male partner and living with
829 that male partner, (d) has not yet participated in couple HIV testing during this pregnancy, and (e) not in
830 an HIV-positive concordant relationship. Male partners are the person identified by the pregnant woman

831 as her primary male partner and should also be 15 years of age or older. More details regarding
832 inclusion of persons younger than 18 years is included in the Inclusion of Children attachment.
833

834 For the qualitative interviews with young women, the inclusion criteria are: (a) 15-24 years of age (b) at
835 least 12 months postpartum (c) willingness/ability to give informed consent. For the qualitative
836 interviews with women who have experienced IPV, the inclusion criteria are: (a) experience of IPV
837 during the recent pregnancy and/or postpartum (b) ≤24 months postpartum (c) willingness/ability to give
838 informed consent.
839

840 *Collaborating sites where human subjects' research will be performed and role of sites in performing*

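### The primary power is computed for 300 couples per arm and counts an all-zero baseline, and the text claims more power at low uptake than Table 2 shows

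*Combined protocol and SAP*

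**What the plan says.** The section on sample size and power calculations describes the primary power as follows: "With three repeated measurements (baseline, 3 months" and 12 months, compound symmetry, and a correlation that was "assumed to be 0.50. With N=300 couples" per arm. It then says "in each arm, our study will have >80"% power to detect "differences in couple testing uptake of 30" to 40% in either intervention arm, against 23% in the control arm, and refers to Table 2. The test is two-sided at 0.017.

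Table 2 gives power for 31/33/35/37% against 23%: 63/84/95/99% at rho 0.50 and 87/97/100/100% at rho 0.10.

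Other sections bear on the inputs:

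- **Enrolment.** Study design gives the arm size as "home-based couple intervention (estimated n=267 couples"), with the same number in the other two arms.
- **Retention.** The Sample size paragraph expects 17% loss, after which "we will still have approximately 664 couples (221 couples in" each group). It also considers 20% loss, leaving 640 couples, calls the power for the primary outcome strong, and cites Table 2.
- **Eligibility.** The woman qualifies only if she "e) has not yet participated in couple HIV testing during this pregnancy". The human-subjects section repeats this as its item "d) has not yet participated in couple HIV testing during this pregnancy".
- **Outcome and model.** Table 1 (Factors to be Assessed) lists couple testing uptake over the observation period as yes/no. Aim 1 fits a marginal model to all longitudinal measures of couple testing. Study design assigns the primary outcome to the midline and final questionnaires (3 and 12 months). Testing is also asked about by phone at 8 weeks after enrolment and at 6 and 18 months after birth.

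**The concern.** Three things do not fit together. The power is computed at 300 per arm, which is 900 couples, while the plan enrols 800. One of the three measurements credited with information is a baseline at which eligibility makes every couple a non-tester. And the sentence summarising Table 2 claims more than the table shows at the low end of its own range.

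What is at stake is the detectable difference that readers are given. If true uptake in an intervention arm were 31-33%, a null result could be read as well-powered evidence of no benefit when it is not.

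**Working it through.** **Method.** Effective couples per arm: n_eff = N × m / (1 + (m − 1) × rho), for N couples and m exchangeable measures. Power = Φ(|p1 − p2| / SE − 2.387), with SE = √{[p1(1 − p1) + p2(1 − p2)] / n_eff}; 2.387 is the two-sided 0.017 critical value.

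**Reproducing Table 2.** With N = 300 and m = 3, n_eff = 900/2 = 450 at rho 0.50 and 900/1.2 = 750 at rho 0.10. For 33% against 23%, the variance sum is 0.2211 + 0.1771 = 0.3982. SE = √(0.3982/450) = 0.02975, and 0.10/0.02975 − 2.387 = 0.975, so power is 83.5%. All cells:

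| rho | 31% | 33% | 35% | 37% | Table 2 |
|---|---|---|---|---|---|
| 0.50 | 62.8 | 83.5 | 94.7 | 98.8 | 63/84/95/99 |
| 0.10 | 86.8 | 97.5 | 99.7 | 100 | 87/97/100/100 |

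Among N = 300, 267, 221 and 213 with m = 1, 2, 3 or 5, only N = 300 with m = 3 reproduces both rows. Pooled variance, or 0.05/3 in place of 0.017, moves results by about one point at most.

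**The sentence against the table.** The plan's own inputs give about 50% power at 30% uptake with rho 0.50, and 76% even with rho 0.10. Power reaches 80% at about 32.6% uptake with rho 0.50 (30.3% with rho 0.10).

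**Sample size.** 800/3 = 267, 664/3 = 221, 640/3 = 213 and 3 × 300 = 900. The 300 may be left over from the earlier recruitment plan: 1,440 × 0.75 × 0.83 / 3 = 299 analysable couples per arm. That origin is inferred, not stated. If it is right, the like-for-like figure now is 221.

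**Baseline.** A value that is zero for every couple has no variance, cannot correlate 0.50 with later waves and cannot show 23% or 31% uptake. Testing in an earlier pregnancy is not excluded, but it lies outside the observation period. The baseline should therefore not be counted in m.

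**Recomputed without baseline, rho 0.50** (power, %, for 31/33/35/37%):

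| Response | 267 | 221 | 213 |
|---|---|---|---|
| Two waves (3 and 12 months) | 51/73/88/96 | 42/63/80/91 | 41/61/79/90 |
| Five post-baseline contacts | 62/83/94/99 | 53/74/89/97 | 51/73/88/96 |
| One value per couple | 38/58/76/88 | 31/49/66/81 | 30/47/64/79 |

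Example: two waves at 221 give n_eff = 442/1.5 = 294.7 and SE = √(0.3982/294.7) = 0.03676. Then 0.10/0.03676 − 2.387 = 0.334, so power is 63%.

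At rho 0.10, two waves give 67/87/96/99 at 267 and 57/79/92/98 at 221. Five contacts give 94/99/100/100 and 89/98/100/100.

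**Split of the loss** at 33%, rho 0.50, two waves: 84 falls to 78 from dropping baseline alone, to 69 from N = 221 alone, and to 63 from both.

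**Large effects, 40% against 23%.** Two or five exchangeable waves give 98% or more. One value per couple at 213 gives about 93%. For two cumulative waves, assume 60% of 12-month uptake q has occurred by 3 months. The couple mean is then 0.8q, with variance [0.6q(1 − 0.6q) + q(1 − q) + 1.2q(1 − q)]/4, which is 0.1776 at q = 0.40 and 0.1271 at q = 0.23. At 213, SE = √(0.3047/213) = 0.0378, and 0.136/0.0378 − 2.387 ≈ 1.21, so power is about 89%.

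**The case against.** The strongest reply is that Aim 1 uses all longitudinal measures, and couple testing is asked about at five post-baseline contacts: 8 weeks, and 3, 6, 12 and 18 months. Counting all five at rho 0.50 and 267 per arm gives 62/83/94/99, almost the published row. This stands as a possible reading, and it shows that the size of the shortfall depends on a definition the plan has not fixed. It does not rescue the text: power at 31% is still 62% at 267 and 53% at 221. Five contacts at rho 0.10 and 267 would exceed 80% at 30% uptake, but the text specifies three measurements and rho 0.50.

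Second, the 221 and 213 columns assume that lost couples contribute nothing. If all 17% loss came after 3 months, two waves would give 48/70/86/95 at rho 0.50. That softens the fall but does not remove it.

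Third, the statement about strong power at 640 couples carries no figure, and the plan says its assumed rates are deliberately below those seen earlier. A difference like that in the self-test trial described under Potential Risks (75.4% against 33.2%) would be detected at 213 per arm with near certainty. A reader might infer that the statement is false; for large effects the documents do not show that. The fair criticism is that it relies on a table computed at 300 per arm.

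Fourth, a reader might infer that the Aim 1 model will average baseline zeros into the response, or is defective because it names no time term. Neither is established. Study design assigns the primary outcome to the two follow-up questionnaires, and the covariate list is left open. The yes/no entry in Table 1 may likewise describe each assessment.

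**Conclusion.** The point holds as a correction to the stated power. Table 2's couple-testing rows are right for their inputs, but 300 couples per arm and an informative baseline do not belong to this trial. The claim of more than 80% power across 30-40% uptake contradicts Table 2 at the stated rho.

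At rho 0.50 with the 3- and 12-month waves, 80% power needs about 34% uptake at 267 per arm and about 35% at 221, against 32.6% with the plan's inputs. These figures rest on exchangeable waves, constant uptake across waves and the plan's control rate of 23%. Lower rho or more contacts raises power; cumulative waves or a single value per couple lowers it.

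A reader might conclude that the trial is underpowered. The documents do not support that: at 40% uptake power is about 89% or more under each post-baseline reading examined. What is wrong is the stated detectable difference. It should be fixed, but it does not threaten the trial.

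**What to change.** 1. State which post-baseline measures form the primary response (the 3- and 12-month questionnaires, all five contacts, or one value per couple by a named visit). Say whether each wave is cumulative or covers only the interval since the last, and that baseline is not in the response.
2. Recompute the two couple-testing power rows of Table 2 on that basis at 267, 221 and 213 per arm, for rho 0.50 and 0.10.
3. Correct the sentence claiming more than 80% power for 30-40% uptake.
4. In the Sample size paragraph, tie the statement about strong power at 640 couples to the recomputed figures and name the uptake for which it holds.

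The cost is some SAP wording and two recomputed rows. Enrolment, data collection and the planned GEE stay as they are. The downside is a lower stated power.

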 599 relationship dynamics and social consequences. We will refer to the parameter estimates for these
 600 three covariates as Estimates B. We will then determine the direct and indirect effects of the treatment
 601 on each of the outcomes in Aims 1 and 2, with
 602 corresponding standard error estimates
 603 determined using bootstrap methods as
 604 described by Whittle, et al.[165] These models
 605 can also be adjusted for any potential
 606 confounders that are discovered, although we
 607 expect the randomization to account for a
 608 majority of any potential confounding.

609 **Supplementary dyadic analyses for Aims 1**
 610 **and 2:** Analyses with intact dyads enable
 611 investigation of couple-based research
 612 questions of how relationship dynamics affect
 613 behavior change in partnerships. For example,
 614 we might investigate whether one's own
 615 relationship satisfaction or one's partner's
 616 relationship satisfaction is more associated
 617 with couple testing uptake. To that end, we will
 618 extend the analyses described above to
 619 include actor and partner effects for covariates
 620 and mediators. *Actor effects* describe the
 621 influence that one's standing on independent or mediating variables of interest (e.g., communication,
 622 intimacy) has on one's own dependent variables (e.g., virologic control) whereas *partner effects*
 623 describe the influence that one's standing on independent variables has on the dependent variables of
 624 one's partner (e.g., partner's virologic control). This technique illuminates the effects that partners in
 625 intimate relationships can have on both their and their partner's behavior. In order to fit an actor-
 626 partner interdependence model (APIM)[166] to our data, we will change our GEE model to a random-
 627 effects model so that we can include a random effect for each couple, that will allow us to divide the
 628 variation in outcomes into within- and between-couple effects. Auto-regressive errors will be assumed
 629 for the longitudinal measures.

630

631

TABLE 3. AIM 2 QUALITATIVE INTERVIEW TOPICS

Theme	Topics
Contraceptive Use	(1) Knowledge and use of contraceptives before current pregnancy and postpartum
Male partner support	(2) Support and dependability of male partner for maternal and child health
Health Care Utilization	(3) Barriers to utilization of health care services for pregnant women and partners
Interventions	(4) perceptions of the home visits for couples and the HIVST kit interventions
IPV	(5) Perceptions of change in violence and the role of pregnancy and HIV in IPV
HIV Care and Treatment	(6) Perceptions of change in HIV care and treatment over pregnancy and postpartum

632 Qualitative data will be analyzed to elucidate themes and lessons to further inform our quantitative
633 analysis (Table 3). Interviews will be audio-recorded and transcribed, translated (if necessary), and
634 then coded and analyzed using a thematic analysis approach.
635

636 **Accounting for potential missing data.** We will also investigate and address incomplete data issues
637 in our sample. Missing data within and between each wave of measurement should be minimal due to
638 our careful interviewer training and cohort retention. However, intermittent missing responses are
639 inevitable and some participants will be lost to follow-up. Our GEE models for Aims 1 and 2 make the
640 assumption that missing data occur completely at random (MCAR). We will use univariate analyses
641 such as chi-square and t-tests to assess whether individuals with complete data for any given analysis
642 are different from those with incomplete data. These analyses will be extended to explore differential
643 attrition by intervention group membership using logistic regression or analysis of variance (ANOVA)
644 models. If our assumption of MCAR appears questionable, we will model the missingness pattern with
645 logistic regression to estimate the probability of each subject's data is missing, conditional on their
646 observed data. We can use these weights in an inverse-probability weighted GEE model and compare
647 the results to those produced from models using only the observed data.

648 **Sex as a biological variable.** This study includes both men and women all analyses described above
649 will be run separately by sex assigned at birth, with the exception of the dyadic analyses, which build in
650 participant sex intrinsically, since we will use APIMs for distinguishable dyads distinguished by gender.
651

652 **Cost-Effectiveness Analysis for Aim 3:** We will assess the cost-effectiveness of the home-based
653 couples intervention compared to two less resource-intensive strategies of HIVST kits and standard
654 care. We hypothesize that this community-based intervention will prove to be a cost-effective strategy
655 compared to the alternative strategies. However, cost-effectiveness might be sensitive to the intensity
656 of services provided, levels of compensation, extent of training, levels of adherence to ART treatment,
657 and other attributes. We will develop a decision analysis model using Tree Age Pro 2017 software
658 (Williamstown, MA, USA). We will use data on costs, changes in HIV status, and mortality to provide
659 inputs into a modified Markov model allowing for both transitions between health states and the
660 occurrence of transient adverse health outcomes. Markov models are among the most frequently used
661 modeling techniques in clinical decision analysis and health-economic evaluation, and are particularly
662 helpful when a decision analysis involves the analysis of risk over long periods of time.[167, 168] The
663 modification we propose will be a state transition model. State transition models combine Markov health
664 state transitions with the probability that individual will experience transient events that lead to either a
665 different health state (e.g. HIV transmission) or that can carry significant costs or mortality risk, such as
666 hospitalization for an opportunistic infection. State-transition models have been utilized in many
667 different populations and diseases, including diabetes, cardiovascular disease, HIV and malaria.[169-
668 171]

669 The final integrated decision model will consist of two parts. In the first part, a couple consisting of a
670 pregnant woman in antenatal care and her male partner, will be assigned to an arm of the decision
671 model (couple home visits, HIV self-test kits, standard of care). The probabilities of health state
672 transitions (e.g. changes in HIV status, viral load suppression, death) and adverse events will differ
673 based on the assigned arm of the decision model. Each woman and male partner enters the model as
674 HIV-negative or HIV-positive. Once a participant enters a new health state (HIV transmission), they
675 remain in that health state until suffering a next event (HIV transmission of a partner or death). In the
676 second part of the model, infant's transition states are considered (HIV-positive, HIV-negative, died).
677 These two parts will then be integrated into one overall model.

[figure not shown]
678 **Cost-effectiveness analytical plan:** In our analysis, we will follow The WHO Guide to Cost-
679 Effectiveness Analysis for the conduct of CEA that is most applicable to developing countries.[172] To
680 determine the cost-effectiveness of the intervention, we will calculate **incremental cost-effectiveness
681 ratios (ICERs)** for the intervention versus each comparator (standard of care; distribution of HIV self-
682 test kits). The numerator of the ratio is the difference in costs expressed in US (purchasing parity
683 adjusted) Dollars; the denominator is the difference in effectiveness.[172, 173] A 10-year time horizon

684 will be used because an extrapolation beyond this would be associated with substantial increases in
685 uncertainty as to future developments in HIV prevention and treatment, as well as the lasting
686 effectiveness of the intervention. ICERs will be compared to the gross domestic product (GDP) as per
687 WHO recommendations to derive the following three categories of cost-effectiveness: highly cost-
688 effective (less than GDP per capita), cost-effective (between one and three times GDP per capita), and
689 not cost-effective (more than three times GDP per capita).

690 Following WHO Guide[172, 174], **the effectiveness** of the intervention will be assessed using the
691 Disability Adjusted Life Year (DALY) as the unit of effectiveness. One DALY represents a year of
692 healthy life lost due to death or disability.[175] We will calculate the DALY as the sum of the years of life
693 lost (YLL) and the years lost due to disability (YLD) that would be saved for each HIV infection averted
694 by study arm based on estimates and disability weights from the Global Burden of Disease (GBD).[176] We
695 will calculate the direct **costs** of each strategy utilizing established guidelines for costing HIV
696 interventions[177, 178] from a program perspective using micro-cost techniques. Cost estimation will
697 involve a uniform cost data collection protocol at each study site. We will conduct observations and
698 interviews with purposively selected sample of health care providers, study and assistant study
699 coordinators, finance and administration officers, to identify program activities on which resources were
700 spent. Expenditures will be classified in one of four categories; (i) personnel (including fringe benefits);
701 (ii) recurring supplies and services; (iii) durable equipment; and (iv) facility space. The costs of the
702 program will be identified through interviews with administrative, finance and human resources officers,
703 supplemented by direct observation in a limited number of formal “time and motion” studies. Costs for
704 equipment and facility space (likely a small portion of total costs) will be amortized on a straight-line
705 basis over their expected useful life assuming no salvage value. Other costs considered include
706 laboratory, medication, and healthcare costs. We will account for costs related to increased use of
707 PrEP, HIV or pregnancy-related services. Research costs (e.g. costs related to consenting and
708 research-participation), any medical costs incurred offsite, or higher-level program costs incurred by the
709 county/national government or donors will be excluded from the programmatic costs. Costs and DALYs
710 will be discounted at a 3% rate.[172]

711 A key element of cost-effectiveness analysis involves properly accounting for the uncertainty
712 associated with the ICER. Such ratios are estimates based on a sample of individuals. They are subject
713 to sampling error, and performing the same trial over and over would lead to different estimates of the
714 ratio. A variety of **sensitivity analyses** will be used to assess the performance of our state transition
715 models.[172] One-way sensitivity analyses will be used to determine which model parameters are most
716 important in determining whether the intervention can be considered cost-effective. Some anticipated
717 parameters include certain clinical practice situations such as decreased testing, initiation, adherence
718 and retention into care, and varying costs of inputs, particularly for the antiretrovirals. Markov Chain
719 Monte Carlo probabilistic sensitivity analyses simulations will then be used to test the robustness of the
720 model findings to uncertainty in the parameter inputs.

721 722 TIME FRAME

723
724
725

726 Aim 1 of this study is to determine the impact of a couples-focused home-based intervention on our
727 primary outcome of couple HIV testing for pregnant women and their male partners as compared to
728 HIV self-test kits for couples and standard care. There is a need to understand how COVID-19 has
729 influenced the Jamii Bora study, participating health facilities, and the study participants. There is also a
730 lack of data on how the new coronavirus has affected research teams and studies, both in their
731 perceptions of the pandemic and its potential effects on participants' health and accessing resources.
732 We propose a standard of care health facility assessment, to assess the impact of the COVID-19
733 outbreak on standard care related to the HIV testing and counseling services for pregnant women and
734 male partners, and compare this to service provision in the pre-COVID-19 period. Data will be collected
735 for the period January to when the COVID-19 curve in Kenya starts to flatten. These data will be
736 collected from registers and electronic medical records from the eighteen health facility sites in Kisumu
737 and Migori counties. Additionally, we will survey our study staff and staff from other HIV prevention and
738 treatment studies in the region to further understand the effects of COVID-19 on participants as well as
739 staff to help the studies construct a positive response to the epidemic.

740

741 **COVID-19 RESTRICTIONS**

742 To protect study participants, their families and research staff from the risk and spread of COVID-19,
743 the study will adhere to all Ministry of Health directives and well as SERU guidelines aimed at mitigating
744 the spread of COVID-19. We will inform research participants of requirements to undergo COVID-19
745 screening and reporting of screening results to the local public health authorities whenever the results
746 may point at a possible infection with the disease, for their benefit. We will also provide participants and
747 staff with 3 ply face masks, avail hand washing stations at the study sites, and provide sanitizers. We
748 will pre-screen participants before physical contact, check temperature and observe social distancing
749 requirement of 1.5 meters during face-to -face interaction with participants. Pens used for consenting
750 will be disinfected before and after individual use. We will inform the participants of the measures that
751 we will be taking during any form of face-to-face contact and unconditionally will respect their
752 preferences in terms of in-person versus remote study visits. We will also have daily mandatory
753 screening for staff who are making contact with participants and only those without any COVID-19
754 symptoms will be allowed to make contact with participants. The staff will also disinfect furniture and
755 sanitize their hands after every contact with a participant.

756

757 **ETHICAL CONSIDERATIONS**

758 This protocol will be reviewed by the Institutional Review Boards (IRB) of the University of Alabama at
759 Birmingham and the University of Michigan, Ann Arbor. In Kenya, the protocols will be reviewed by
760 KEMRI Scientific and Ethics Review Unit (SERU) (FWA# 00002066). We will ensure that all procedures
761 conform to US, Kenyan, and international ethical standards regarding research involving human
762 subjects.

763 The proposed research will be conducted in collaboration with investigators of the Kenya Medical
764 Research Institute (KEMRI), county Ministry of Health (MoH) teams and clinics (see letters of
765 support), and U.S. President's Emergency Plan for AIDS Relief (PEPFAR) partners in counties in the
766 former Nyanza Province in southwestern Kenya. Our team already has long-standing positive
767 relationships with the local MoH teams and the study communities. Our intervention strategy takes
768 advantage of the extensive existing infrastructure of these partners and is a direct response to needs
769 identified by MoH and local clients and staff in the Nyanza Region. We have developed our research
770 strategy after extensive consultations with MoH county teams and other local partners. Prior to our pilot
771 study for this intervention, we conducted a series of meetings with the leadership and program staff to
772 obtain their input and guidance as to the best methods for delivering a couples intervention for pregnant
773 women and their male partners, and how such an intervention could best be incorporated into existing
774 support of these health facilities. Before beginning the proposed study, we will also consult with local
775 health workers, community leaders, and representatives of community groups (including HIV clinic
776 workers).

778 patient groups) in all study communities. We have purposely selected communities with active
779 Community Units for participation in this study in order to assure close consultation with the local
780 communities. The proposed research builds on our findings and our experience protecting human
781 subjects in our other studies conducted in rural Nyanza and other relevant settings, including the "A
782 Home-Based Couples Intervention to Enhance PMTCT and Family Health in Kenya" study, in which we
783 developed and piloted the intervention to be tested in the currently proposed R01 study
784 (R34MH102103, PI: [name]), the Maternity in Migori and AIDS Stigma (MAMAS) Study (NIMH
